2.3. SAMPLE SIZE CALCULATION

The study primary objective will be met in case the null hypothesis that the success rate of the “In-Clinic LVAT” is lower than 90% is rejected.

The following assumptions were made to calculate the sample size:

- Power = 80%
- One-sided alpha = 2.5%
- Null Hypothesis proportion of success-rate (target) = 90%

LEVEA – Statistical Analysis Plan

- Expected success-rate = 95%

With these assumptions, it is required to carry out at least 231 LV vector tests. As we will have 5 different pacing vectors for each subject, we will need 47 ($\sim 231/5$) subjects.

An attrition rate of 20% is expected for this study.

Thus the number of subjects needed to be enrolled to obtain 47 evaluable subjects = $47/(1-0.2) = 59$ subjects.

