6.3. INTENTION TO TREAT POPULATION (ITT)

The Intention To Treat (ITT) population consists of all subjects from EP with at least 1 eligible complete LV Vector Tests at M0 or M1 visit.

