9.1.2. STATISTICAL TEST OF PRIMARY ENDPOINT

The Null hypothesis: Success rate of the “In-Clinic LVAT” feature $< 90\%$.

The alternative hypothesis: Success rate of the “In-Clinic LVAT” feature $\geq 90\%$.

Each LV vector test will be categorized as a success if the automatic and manual LV threshold test has an equivalent LV threshold value, and failure otherwise. The definition of an equivalent LV threshold value is provided above in Table 4.

The success rate of “In-Clinic LVAT” test is defined as: Number of successes/Total Number of completed LV vector tests (excluding the tests for which Manual test is missing).

A one-sided exact binomial test for proportion at 2.5% level of significance (alpha) will be performed to test the null hypothesis for the primary endpoint. The null hypothesis will be rejected if the p-value is less than 0.025.

The estimate of success rate and 95% exact CI (Clopper & Pearson, 1934) will be presented.

LEVEA – Statistical Analysis Plan

DECOMPOSITION OF PRIMARY ENDPOINT SUCCESS RATE BY LV VECTOR AND BY CONFIGURATION

Total number of completed and successful LV vector tests considered for the Primary Analysis will be presented by:

- i. LV vector tests considered with DDD A-test LV pacing configuration at M0 visit. The break up of the five LV vectors will also be presented.
- ii. LV vector tests considered with VVI test LV pacing configuration at M0 visit. The break up of the five LV vectors will also be presented.
- iii. LV vector tests considered with DDD A-test LV pacing configuration at M1 visit. The break up of the five LV vectors will also be presented.
- iv. LV vector tests considered with VVI test LV pacing configuration at M1 visit. The break up of the five LV vectors will also be presented.

Only those LV tests will be considered for which manual tests are non-missing. For number of LV vector tests “completed”, the percentage will be calculated based on ITT.

For number of LV vector tests “Successful”, the percentage calculated based on number of LV vector tests “completed”.

All LV vector test results will be listed.

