9.1.3. SUPPORTIVE AND SENSITIVITY ANALYSIS FOR PRIMARY ENDPOINT

- i. Bayesian analysis will be performed to calculate the probability that the success rate is greater than or equal to 90%. A non-informative prior for the success rate ($\sim \text{Beta}(1,1)$) will be assumed. Thus, if x successes out of n completed LV vector tests (excluding the tests for which Manual test is missing) is observed, then success rate will have a posterior distribution $\text{Beta}(x+1, n-x+1)$. A 95% credible interval will also be calculated for the success rate. The prior and the posterior density function will also be plotted.
- ii. In case the number of completed LV Vector Tests (M0 and M1 combined) is less than 231 and the primary endpoint null hypothesis is rejected, Tipping Point Analysis will be performed. Primary analysis will be repeated by shifting the status of subjects with missing primary endpoint value in order to assess the combination of results which will move the performance results from significant to non-significant. A 95% CI will be presented for each shift parameter.
- iii. The Primary analysis will be repeated excluding the subjects with major protocol deviations from the subjects considered for the primary analysis.

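### The tipping-point analysis is worded to shift subjects, but the primary outcome is per LV vector test, so as worded it may vary few or none of the missing outcomes

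*SAP*

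**What the plan says.** SAP 9.1.2 sets the unit of the primary outcome: "Each LV vector test will be categorized as a success if" the automatic and manual thresholds are equivalent. The rate is successes over completed tests that have a manual value. An exact one-sided binomial test at 2.5% compares it with 90%. The sample size uses the same unit: "it is required to carry out at least 231 LV vector tests" (SAP 2.3), converted to people by "As we will have 5 different pacing vectors for each subject, we will need 47" subjects.

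SAP 9.1.3 item ii applies when fewer than 231 tests are completed and the null is rejected. It then states: "Primary analysis will be repeated by shifting the status of subjects with missing primary endpoint value", to find where significance is lost. It names no population, defines no status for a subject, and does not say how many tests a shifted subject adds.

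The primary analysis runs on ITT (Protocol 8.1 and 8.2; SAP 6.7). SAP 6.3 limits ITT to evaluable-population subjects "with at least 1 eligible complete LV Vector Tests at M0 or M1 visit". SAP 6.2 has already removed subjects who terminate before M0. The only success status defined for a subject is the ancillary endpoint in SAP 12.2 (at least one successful test).

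**The concern.** A tipping-point analysis should vary the outcomes that are missing. Here these are LV vector tests, and many gaps can be expected in subjects who have other vectors. SAP 5.7 foresees tests that are aborted, interrupted or return no value, and SAP 9.1.1 foresees missing manual values. A subject with three of five vectors evaluable does not lack a primary endpoint value, so item ii as worded leaves the other two alone.

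Nothing else covers the gap. Protocol 8.5.1 allows no imputation, the Bayesian analysis uses completed tests only, and SAP 9.1.3 item iii only removes subjects with major deviations. The trigger is within easy reach: 47 evaluable subjects give 47 x 5 = 235 tests, and five missing tests bring that to 230.

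**Working it through.** **1. The plan's own figure.** Inputs from SAP 2.3 and 9.1.2: null rate 0.90, expected rate 0.95, one-sided alpha 0.025, power 80%, exact binomial. At n = 231 the smallest rejecting count is 217: P(X >= 217 | 0.90) = 0.0239 and P(X >= 217 | 0.95) = 0.816. This is the smallest n with exact power of at least 80%. Then 231/5 = 46.2, rounded up to 47, and 47/(1 - 0.2) = 58.75, rounded up to 59. The plan's 231, 47 and 59 all reproduce, in units of tests.

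**2. Where gaps are likely to fall.** Protocol 2.2.1(b) reports a comparable automated algorithm: 780 of 992 vectors measured, and at least one vector in 62 of 65 subjects. Assuming equal vectors per subject (992/65 = 15.3), the 3 wholly missing subjects account for about 3 x 15.3 = 46 of the 992 - 780 = 212 missing vectors. The other 166 (78%) were in partly tested subjects, the kind of gap that item ii as worded does not vary.

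**3. Assumed counts.** The documents give no missing-data counts. Assume 225 retained tests, below the trigger of 231. The ceiling is 59 x 5 = 295, so up to 295 - 225 = 70 tests are missing. All p-values are P(X >= x | n, 0.90) and treat tests as independent, as the plan does.

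**4. No wholly missing subject.** Suppose all 59 subjects have at least one retained primary test.
- Shifting subjects: there is none to shift, so 214/225 stays at p = 0.0041.
- Shifting tests, with f failures among 70, the count is (214 + 70 - f)/295. At f = 8, 276/295 gives p = 0.0213. At f = 9, 275/295 gives p = 0.0351. The result tips at 9/70 = 13% failures. With all 70 failing, 214/295 gives p near 1.

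Over a range of observed rates:

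| Observed | Shifting subjects | Shifting tests: tips at | Implied failure rate |
|---|---|---|---|
| 214/225 (95.1%) | never tips | 9 of 70 | 13% |
| 216/225 (96.0%) | never tips | 11 of 70 | 16% |
| 218/225 (96.9%) | never tips | 13 of 70 | 19% |
| 220/225 (97.8%) | never tips | 15 of 70 | 21% |

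**5. Some wholly missing subjects, added back.** Take 218/225 with 5 wholly missing subjects, all counted as failures.
- One unit per subject: 218/230, p = 0.0067, still significant.
- Five tests per subject: 218/250, p = 0.94.

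On either rule the remaining 70 - 25 = 45 tests, missing in partly tested subjects, are not varied. The SAP does not choose between the rules.

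**The case against.** The best defence is that the SAP uses subjects loosely to mean tests. The version 1.1 entry in the change history (SAP 3.2) restricts comparisons to LV tests with a manual value, while SAP 10.2, 10.4, 11.1 and 12.2 express the restriction in terms of subjects. Item ii's trigger is also counted in tests, and it repeats a per-test analysis. If missing tests are what is meant, the fault is wording only. This stands as a possible reading, but the text does not settle on it.

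A reader might go further and infer that the analysis makes the result look far more robust than it is. For example, at 209/220 (p = 0.0055), shifting 75 missing tests tips at 9 (12%; 275/295, p = 0.035), while 12 missing subjects counted as one unit each tip at 4 (33%; 217/232, p = 0.040). The documents do not support this as a general claim. No passage says that a subject enters as one unit, and the comparison changes the missing set as well as the unit. If the 12 subjects carry five tests each, the result tips at 2 of 12 (17%; 259/280, p = 0.094; 1 of 12 gives 264/280, p = 0.0075). Shifting the same 60 tests singly tips at 8 (13%; 261/280, p = 0.040). The difference is then small. Nor does one-unit counting always hide fragility: with 10 wholly missing subjects all failing, 220/225 becomes 220/235, p = 0.035.

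It would also be too strong to call the analysis empty. Item ii names no population. Even an ITT subject can lack a primary value if the complete tests are all DDD P-test, all on other vectors, or all without a manual value.

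**Conclusion.** The unit mismatch is real and should be corrected. Followed literally, item ii omits vectors missing in partly tested subjects, and ITT leaves few or no wholly missing subjects to shift. In the assumed case of 225 retained tests with no subject wholly missing, it varies nothing, while a test-level analysis tips at 9 to 15 of 70 missing tests. The size depends on the unknown pattern of missing data and on which reading is programmed. The figure of 70 is an upper limit, since the evaluable population may be smaller than 59. This is a conditional sensitivity analysis, so the primary test, its alpha and the sample size are unaffected.

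**What to change.** In SAP 9.1.3 item ii, replace the reference to subjects lacking a primary value with missing primary LV vector tests, and add:
- **Expected set:** the five common vectors (SAP Table 7) for each subject in the evaluable population, minus the tests analysed. Using every included subject would bring in those excluded on the lead criterion, who may not be able to provide all five vectors. Add subjects who terminate before M0 as a stated extra scenario.
- **Shift:** vary failures from 0 to all missing tests, with the same exact test. Report the tipping number and the implied failure rate among missing tests.
- **Breakdown:** report separately the tests missing because no manual value was available and the tests not attempted or incomplete. The second group lies outside the endpoint's denominator of complete tests, so including it answers a somewhat different question.

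The cost is SAP wording and minor programming. The reported tipping point may be less favourable.

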10. SECONDARY EFFICACY ANALYSES

Secondary and Ancillary endpoints will be assessed at all visits using descriptive statistics. Point estimates and exact CI (Clopper & Pearson, 1934) will be presented wherever possible.

Whenever a Statistical test is performed for a Secondary Endpoint, it is of hypothesis generating and descriptive in nature.

10.1. ASSESSMENT OF DIAGNOSTIC ACCURACY OF “IN-CLINIC LVAT” TEST AT M0 VISIT: INDEPENDENT REVIEWER VALIDATION OF LV THRESHOLD VALUE PROVIDED BY ALGORITHM

This endpoint is the number of accurate determination of the LV pacing threshold value provided by the algorithm feature and an independent reviewer, on all LV pacing vectors and all pacing configurations available at M0 visit.

Diagnostic accuracy is defined as an accurate adjudication by an independent reviewer of LV threshold value provided by the algorithm. The adjudication is based on capture and loss of capture analysis on electrogram strips recorded and stored during “In-Clinic LVAT” tests. The LV threshold value provided by the algorithm compared to the reviewer adjudication is considered accurate if the difference is within ± 1 step (meaning ± 0.25 V if threshold < 2.5V, else ± 0.5 V as measured). The definition of an Accurate LV threshold value is provided above in Table 5.

In case the algorithm and the reviewer adjudication provide both a LV threshold value equal to “>5V” (the LV vector test has resulted in “no capture” or “threshold value higher than 5V at starting amplitude), the LV threshold value is considered accurate. Number and percentages of “accurate” and “inaccurate” matches will be presented along with the exact 95% CI (Clopper & Pearson, 1934).

This analysis will be performed on M0-ITT population.

Decomposition of Diagnostic Accuracy by LV Vector and by LV pacing configuration

Total number of attempted, completed, and accurate LV vector tests will be presented by LV vector for each LV pacing configuration.

For the LV tests performed for subjects with either IS1 and IS4 leads (six LV vectors common to IS1 and IS4), the percentage for the number of LV vector tests “attempted”, will be calculated based on the number subjects implanted with either IS1 and IS4 leads.

For the LV tests performed for patients with IS4 leads (eight LV vectors pertaining only to IS4), the percentage for the number of LV vector tests “attempted”, will be calculated based on the number of patients implanted with IS4 lead.

For number of LV vector tests “completed”, the percentage will be calculated based on the number of LV vector tests attempted and for number of LV vector tests “accurate”, the percentage calculated based on number of Complete LV vector tests .

A heat plot will be presented for Attempted, Completed and Accurate percentages. If the percentage is > 90%, it will be coloured green, if the percentage is between 75% and 90% (inclusive), it will be coloured brown and if the percentage <75%, then it will be coloured orange.

This will also be listed.

For this analysis, EP will be used considering M0 visit only.

10.2. ASSESSMENT OF THE SUCCESS RATE OF “IN-CLINIC LVAT” TEST AT M0 VISIT: COMPARISON TO MANUAL LV THRESHOLD TESTS RESULTS

This endpoint is the success rate of “In-Clinic LVAT” feature on LV pacing vectors and LV pacing configurations available at M0 visit.

The threshold obtained from the “In-Clinic LVAT” feature, extracted from RTD files, will be compared against manual LV threshold values recorded in the eCRF. The definition of equivalence is same as that of primary analysis.

Test will be evaluated at different LV pacing configuration: DDD A-test, DDD P-test and VVI test. Among all the eligible complete LV Vector Tests collected, only those with a manual LV threshold test performed in the same conditions (same pacing pulse width) at M0 visit and reported in the electronic Case Report Form (eCRF) will be retained.

All analyses performed for this Secondary endpoint will be performed based on manual LV threshold tests results considering data only from M0 visit (except for testing of hypothesis and missing data imputation).

This Secondary endpoint will be based on M0-ITT population.

Decomposition of “In-Clinic LVAT” Success Rate by LV Vector and by LV pacing configuration at M0 visit

Only subjects with non-missing manual data will be considered.

Total number of attempted, completed and successful LV vector tests will be presented by LV vector for each LV pacing configuration.

For number of LV vector tests “attempted”, the percentage will be calculated based on the EP population.

For number of LV tests “completed”, the percentage will be calculated based on the number of LV vector tests attempted.

For number of LV vector tests “Successful”, the percentage will be calculated based on number of Complete LV vector tests.

A heat plot will be presented for Attempted, Complete and Success percentages. If the percentage is > 90%, it will be coloured green, if the percentage is between 75% and 90% (inclusive), it will be coloured brown and if the percentage <75%, then it will be coloured orange.

For this analysis, EP will be used considering M0 visit only.

10.3. ASSESSMENT OF THE SUCCESS RATE OF “IN-CLINIC LVAT” TEST AT M1 VISIT: COMPARISON TO MANUAL LV THRESHOLD TESTS RESULTS

This endpoint is the success rate of “In-Clinic LVAT” feature on LV pacing vectors and LV pacing configurations available at M1 visit.

The analysis performed for this objective will be exactly similar to that performed for Secondary Objective # 2, but for M1-visit.

For this analysis, M1-ITT population will be used.

LEVEA – Statistical Analysis Plan

For the Decomposition analysis, EP will be used considering M1 visit only.

10.4. EVALUATION OF THE APPLICABILITY OF THE ALGORITHM

The algorithm may not be applicable to some subjects, mainly because of a very long inter-ventricular conduction delay (VV delay). A subject is defined as “eligible” if he/she has at least one complete LV vector test in either of the M0 or M1 visit.

The endpoints for the applicability of the algorithm in the population are:

- A. The number and percentage of subjects who are “eligible” to receive the algorithm. Percentage will be calculated based on the total number of subjects included in the EP, that is:

Number of subjects with at least one complete LV Vector Test at M0 or M1 visits/ Total Number of subjects in EP.

- B. For subject having IS1 lead, up to 6 LV vector tests over 3 LV pacing configurations will be attempted for each subject at each visit.

Among all the subjects having IS1 leads, the number and percentage of subjects having no, one, two,..., six Attempted, Completed and Successful LV vector tests will be presented by LV pacing configuration and visit.

Among all the subjects having IS4 leads, the number and percentage of subjects having one, two,..., fourteen Attempted, Completed and Successful LV vector tests will be presented by LV pacing configuration and visit.

Only subjects with non-missing manual data will be considered.

Percentages calculated based on the number of subjects in EP with the respective lead and configuration will be presented for Attempted, Completed and Successful LV tests.

This information will also be presented with the help of histograms.

This analysis will be based on EP.

This will also be listed.

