2.2. AVAILABLE CLINICAL DATA

2.2.1. *Data from similar features*

a. *Medtronic LVCM*

Left Ventricular Capture Management® (LVCM) algorithm is an automatic feature that monitors the pacing amplitude threshold and adjusts LV outputs. This function helps to ensure delivery of CRT, potentially save time in testing and measuring LV pacing thresholds during subject follow-up.

Therefore, it will automatically balance subject safety and device longevity. LVCM customizes LV pacing outputs to match the needs of individual subjects and analyze LV thresholds over time with trends reports. [10-13]

In the study of Crossley et al. [10], 134 subjects (130 analyzed) from 18 centers, already implanted with a CRT-D system, were enrolled in a clinical trial to evaluate the performance of the LVCM algorithm.

At each follow-up, threshold values were measured manually and with LVCM algorithm. The results were then compared on 307 complete threshold measurement pairs (manual and LVCM in-office tests) collected from 107 subjects for the primary endpoint analysis:

- The difference between LVCM in-office tests and manual threshold tests was within one step in 99.7% (306/307) of the attempts with a two-sided 95% confidence interval of [98.2%, 100.0%].
- LVCM in-office test was identical to the manual LV threshold test in 247 out of 307 attempts (80.72%).

b. *Medtronic VectorExpress*

In the study of Johnson et al. [7], the accuracy of an automated pacing capture thresholds algorithm for quadripolar left ventricular leads called VectorExpress was determined. This algorithm provides automatically the pacing threshold value on all selected LV pacing vectors. Evaluation was performed comparing both threshold values provided by the algorithm and measured manually.

Thresholds were measured for 780 of 992 vectors and at least one vector was measured in 62 of 65 subjects. Results were considered as equivalent if the difference of threshold value provided by manual test and the algorithm was:

- Within $\pm 0.5V$ if manual threshold is strictly inferior to 2.5 V, or
- Within $\pm 1.0V$ if manual threshold is between 2.5 V and 6.0 V.

The accuracy of the automatic algorithm VectorExpress compared to the manual pacing test was 95.3%.

c. *Boston Scientific LVAT (Left Ventricular Auto Threshold)*

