The ELEVATE (Evaluation of LEft Ventricular Auto ThrEshold) study is an acute, prospective, multicenter, pilot study designed to characterize the performance of Boston Scientific LVAT (Left Ventricular Auto Threshold) feature, specifically the commanded mode of LVAT. The study compared the threshold value measured

manually to the one provided by LVAT feature using a surface ECG [14]. The commanded mode of LVAT enables to determine automatically the pacing threshold value of a LV pacing vector.

The LVAT algorithm was able to determine a threshold value in at least one of four LV pacing vectors in 69 of 70 (98.57%) subjects.

The accuracy of the LVAT-determined threshold value was quantified using two different metrics. The threshold determined by the algorithm and by the Corelab matched in 233 of 234 tests (99.5%). In addition, the comparison to the manual threshold value was considered as successful (meaning within two voltage steps) in 96.14% of cases.

Another clinical study sponsored by Boston Scientific is ongoing but not recruiting participants. This clinical trial is called Evaluation of Automatic Threshold Algorithms (CAPTIVATE): see <https://clinicaltrials.gov>. The study aims to evaluate the PaceSafe Right Ventricular Autothreshold (RVAT) and Left Ventricular Autothreshold (LVAT) features for AUTOGEN CRT-D devices. The accuracy of the algorithm will be measured for all subjects, by comparing both threshold values provided by the algorithm and by the Corelab at 1 and 3 months follow-ups. The estimated number of subjects to enroll is 170.

The primary outcomes are:

- The evaluation of the system-related complication-free rate.
- The evaluation of the accuracy of the LVAT Ambulatory test: comparison of threshold value of LVAT algorithm and a Corelab (independent physician). The accuracy of the algorithm will be measured for all subjects, at both 1 and 3 months follow-ups.

The secondary outcome is the evaluation of the percentage of LVAT commanded tests that result in an appropriate outcome. Test outcome would be inappropriate when LVAT threshold could not be determined due to a limitation of LVAT feature and might not occur in manual threshold tests.

The completion date of the study is expected to the end of year 2016.

d. Summary of literature from similar devices

Algorithm	% of subjects with at least 1 test during a follow-up	% of complete* test	% successful** test versus manual test	% successful** test versus ECG

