4.1.3. Secondary endpoints

a. Assessment of the diagnostic accuracy of “In-Clinic LVAT” test at M0 follow-up: Independent reviewer validation of LV threshold value provided by algorithm

This endpoint is the number of accurate determination of the pacing threshold value provided by the algorithm feature and an independent reviewer, on all LV pacing vectors and all pacing configurations available at M0 follow-up.

Diagnostic accuracy is defined as an adjudication of LV threshold value provided by the algorithm. The adjudication is based on capture and loss of capture analysis on electrogram strips recorded and stored during “In-Clinic LVAT” tests. The threshold value provided by the algorithm compared to the reviewer adjudication is considered accurate if the difference is within ± 1 step. The reason for incorrect determination of capture/loss of capture (if any) will be reported.

In case several LV Vector Tests were eligible with the same LV pacing vector, in the same pacing configuration, for the same subject, on the same follow-up, only the last one will be considered.

b. Assessment of the success rate of “In-Clinic LVAT” test at M0 follow-up: comparison to manual LV threshold tests results

This endpoint is the success rate of “In-Clinic LVAT” feature on pacing vectors and pacing configurations available at M0 follow-up. The method of analysis is similar to the primary endpoint.

c. Assessment of the success rate of “In-Clinic LVAT” test at M1 follow-up: comparison to manual LV threshold tests results

This endpoint is the success rate of “In-Clinic LVAT” feature on pacing vectors and pacing configurations available at M1 follow-up. The method of analysis is similar to the primary endpoint.

d. Evaluation of the applicability of the algorithm

The algorithm may not be applicable to some subjects, mainly because of a very long inter-ventricular conduction delay. A subject is defined as eligible as soon as one LV Vector Test is complete.

The endpoints for the applicability of the algorithm in the population are:

- The percentage of subjects who are eligible to receive the feature that is the percentage of subjects with at least one complete LV Vector Test at M0 and M1 follow-ups.
- The number of LV Vector Tests attempted, and percentage of completed and successful LV Vector Tests at M0 and M1 follow-ups per subject.

e. Assess the device characteristics in terms of safety and deficiencies

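### SAP 10.4 A reports applicability only as an either-visit rate; rates at M0 and at M1 should be reported separately, and the IS4 count table needs a zero category

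*SAP*

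**What the plan says.** **The endpoint.** Protocol 4.1.3 d gives the first applicability endpoint as "the percentage of subjects with at least one complete LV Vector Test at M0 and M1 follow-ups". Just before the endpoint list it states: "A subject is defined as eligible as soon as one LV Vector Test is complete". That sentence names no visit.

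**The SAP rule.** SAP 10.4 makes a subject eligible "if he/she has at least one complete LV vector test in either of the M0 or M1 visit". Item A then defines the reported ratio as "Number of subjects with at least one complete LV Vector Test at M0 or M1 visits/ Total Number of subjects in EP". Item A gives no separate M0 or M1 figure.

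**The general rule.** Protocol 8.5.2 and SAP 10 both say that secondary endpoints are described at all follow-ups or visits, with confidence intervals where possible.

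**The count tables.** SAP 10.4 B tabulates tests per subject by pacing configuration and visit. For IS1 leads the categories start at none and run to six. For IS4 leads the table is "the number and percentage of subjects having one, two,..., fourteen Attempted, Completed and Successful LV vector tests", with no category for none.

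**Literature background.** The summary table in Protocol 2.2.1 d heads its column as the percentage "of subjects with at least 1 test during a follow-up". The underlying text reports that for one algorithm "at least one vector was measured in 62 of 65 subjects", and that another found a threshold "in at least one of four LV pacing vectors in 69 of 70 (98.57%) subjects".

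**The concern.** The feature is launched at a given follow-up, so the practical question is how often it gives at least one threshold on that day. A subject in whom every test fails at M0 but one completes at M1 counts as fully applicable under 10.4 A. The reported figure therefore describes two chances, not one.

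The SAP is also uneven. The second applicability bullet in Protocol 4.1.3 d uses the same phrase about M0 and M1, and SAP 10.4 B carries it out by visit. Item A carries out the first bullet by pooling the visits.

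At stake is how a secondary, descriptive figure will be read. Someone who sets the 10.4 A percentage beside the protocol's literature rates would compare two visits with one. For IS4 subjects, the group whose additional vectors had not been tested before this study (Protocol 2.3), the count table leaves out the category that shows non-applicability directly.

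**Working it through.** **1. Reproduce the literature rates (Protocol 2.2.1).**
- 62/65 = 95.4%; the summary table prints 95%.
- 69/70 = 98.57%; the summary table prints 98%, which is the figure truncated.

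Both sit under a per-follow-up column heading.

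**2. Relate the either-visit rate to the single-visit rate.** Let p be the share of subjects with at least one complete test at a visit. Take p as equal at M0 and M1, with all subjects attending both. Let φ be the correlation between visits in a subject's outcome. The documents give neither p nor φ, so both are assumptions and are shown over a range with φ from 0 to 1.

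- P(fail at both visits) = (1 − p)² + φ·p·(1 − p)
- P(either visit) = 1 − P(fail at both visits)
- P(both visits) = 2p − P(either visit)

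| Per-visit p | φ = 0 | φ = 0.5 | φ = 0.75 | φ = 1 |
|---|---|---|---|---|
| 80% | 96.0% | 88.0% | 84.0% | 80.0% |
| 85% | 97.8% | 91.4% | 88.2% | 85.0% |
| 90% | 99.0% | 94.5% | 92.3% | 90.0% |
| 95.4% | 99.8% | 97.6% | 96.5% | 95.4% |

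The cells are either-visit rates. At p = 90% the formula reduces to 99% − 9 points × φ, so the excess over the single-visit rate runs from 0 to 9 points. At p = 95.4% it runs from 0 to 4.4 points. It is zero only when no subject fails at one visit and passes at the other.

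**3. Compare the three readings of the protocol phrase at p = 90%.**
- Per visit: 90%.
- Either visit: 90% to 99%.
- Both visits: 1.80 − (0.99 − 0.09φ) = 0.81 + 0.09φ, that is 81% to 90%.

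The SAP has taken the reading that can only be the highest.

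**4. When would p = 90% look better than the literature?**
- Above 62/65: 0.99 − 0.09φ > 0.9538, so φ must be below about 0.40.
- Above 69/70: 0.99 − 0.09φ > 0.9857, so φ must be below about 0.05.

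In reverse, an either-visit rate of 95.4% corresponds to a per-visit rate of 78.5% (φ = 0), 91.5% (φ = 0.5) or 94.0% (φ = 0.75).

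**5. Can the per-visit figure be recovered from other planned output?**
- SAP 7.1 reports the sizes of M0-ITT and M1-ITT, which require at least one eligible complete test at the visit. These are disposition counts as a percentage of the included population, with no confidence interval, and are not labelled as this endpoint.
- SAP 10.4 B is split by pacing configuration and limited to subjects with non-missing manual data. The share with at least one complete test in any configuration cannot be added up from it.
- SAP 13.3 is analysed by visit, but its definition of an eligible subject names no visit.

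**6. Can the IS4 zero category be recovered?** The denominator in 10.4 B is EP subjects by lead and configuration, so a remainder can be computed. Because of the manual-data restriction, that remainder may mix subjects with no completed test with subjects who lack manual data or missed the visit.

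**The case against.** The strongest reply is that the SAP departs from nothing. The protocol's eligibility sentence asks for one complete test and names no visit, and the phrase about M0 and M1 can mean each visit, both visits or the two together. This stands. A reader might infer that the SAP contradicts the protocol and should have declared a change in SAP 3.1. The documents do not support that for the visit rule.

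A second reply is that the excess may be negligible. Both documents name a very long inter-ventricular delay as the main cause of non-applicability. That is a subject trait, so the same subjects should tend to fail twice. This also stands: 99% at p = 90% is an upper bound under independence, not an expectation.

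Third, the literature rates are background. No comparison of applicability with them is planned and no applicability goal is set. Nor would a per-visit rate be fully like for like, since one literature rate rests on four vectors while an IS4 subject here can have up to 14 vectors in three configurations. A reader might infer that the rule is there to make the feature beat its comparators; nothing in the documents says so. An IS4 subject may have up to 14 × 3 × 2 = 84 tests in which to qualify, but only the factor of two comes from the visit rule.

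Fourth, per-visit information is not hidden, since the M0-ITT and M1-ITT counts will be shown. That stands in part. Those counts give numerators, but not the endpoint with an interval and a matching denominator. Likewise the missing IS4 category leaves the 10.4 A ratio untouched, but it is still a gap in 10.4 B.

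**Conclusion.** The point holds as a reporting gap in a descriptive secondary endpoint. SAP 10.4 A settles an ambiguous protocol phrase in the most lenient way and gives no visit-specific estimate. Both documents' general rule for secondary endpoints, and the SAP's own handling of the companion bullet, point to reporting by visit.

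The direction is certain: on the same subjects with complete follow-up, the either-visit rate is equal to or above the rate at each visit. The size is not known. At an assumed 90% per visit the excess is 0 to 9 points, for example 2.3 points at φ = 0.75, and the low end is more plausible given the stated cause. These figures assume equal rates at the two visits, non-negative correlation and full attendance at M1.

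It would go too far to say that applicability is inflated by a known amount or that failures are concealed. The supported statement is that the either-visit rate answers a different question from the single-visit rate and should not be read against per-follow-up literature figures. The primary endpoint is not affected.

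**What to change.** **SAP 10.4 A.** Report the number and percentage of subjects with at least one complete test at M0 and, separately, at M1, each with an exact 95% CI. State the denominator for each and how subjects who missed the visit are counted. The denominator needs to be explicit because Protocol 8.2 assigns applicability to the included population, whereas SAP 10.4 uses EP. Keep the either-visit rate, and add the both-visit rate, as labelled extra rows. Say in one sentence how the protocol phrase about M0 and M1 has been read.

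**SAP 10.4 B.** Add the zero category for IS4 subjects, as already given for IS1 subjects.

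**Cost.** SAP wording and a few table rows, with no new data. The headline applicability figure may be lower than under the current rule.
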